Recovery from deficient sleep has been rarely studied, but we and others have shown that after a single episode of sleep restriction or total sleep deprivation, the inflammatory marker IL-6 (plasma and mRNA levels) do not normalize after one night or even two nights of recovery sleep⁴². Furthermore, preliminary data from our ongoing study suggest that the expression of IL-6 by monocytes never fully returns to baseline during brief recovery sleep periods occurring during a longer period of sleep restriction (see **Figure 3**). From this perspective, (and as depicted in **Figure 2**), we expect that during a single night of recovery sleep (typical for insomnia^{31;41}) between successive episodes of experimental insomnia, the ability of inflammatory systems markers to return to baseline will progressively decline, and their sensitizing actions will prevent normalization of pain measures (i.e., pain thresholds and temporal summation of pain). Similarly, we assume that recovery of the pain-inhibitory system will not be fully achieved during a single night of good sleep in-between experimental insomnia episodes, leading to a situation where the next exposure to insomnia ‘hits’ an incompletely recovered system. As depicted in **Figure 2**, we expect that the ability of the pain-inhibitory system to return to baseline will progressively decline during successive recovery sleep periods, leading to less habituation to pain over time, as manifested in a failure to experience supra-threshold pain as less intensive across day-to-day exposure.

Summarizing the importance and implications of the knowledge gained:

- (1) While it has long been known that insomnia is highly comorbid with chronic pain conditions, we still do not have a good understanding of the underlying mechanisms. To our knowledge, this proposal will be the first to investigate the mechanistic roles of two processes that we hypothesize to underlie insomnia-induced pain processing abnormalities: (a) Inflammatory-induced sensitization of the nociceptive system and (b) pain-inhibitory-induced habituation.
- (2) Considering the high life-time prevalence of insomnia and chronic pain, as well as their high comorbidity, mechanistic knowledge is essential for the development of specific targets to prevent or ameliorate pain amplification due to insomnia. As it is unlikely that we will eradicate insomnia in

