To summarize, this proposal has various innovative aspects in the investigation of pain amplification in response to insomnia: (1) Taking a mechanistic approach (inflammatory-induced sensitization, pain-inhibitory induced habituation to pain), rather than continuing to characterize the general association between insomnia (or sleep deficiency in general) and pain. (2) Studying inflammatory and pain-inhibitory systems changes within a real-life model consisting of repeated exposure to experimentally-induced insomnia symptoms, rather than studying changes within short-term models of sleep restriction or deprivation of a few days. (3) Investigating the ability of system changes to recover from repeated exposure to experimentally-induced insomnia symptoms, rather than concentrating only on the effects of deficient sleep.

B3. DESCRIPTION OF RESEARCH PROTOCOL

A. Study Design – Overview, Methods, Procedures

Proposed Research Plan.

The overarching hypothesis of this research is that repeated exposure to experimentally-induced insomnia symptoms increases vulnerability to chronic pain by promoting two processes: (1) sensitization of the nociceptive system via a progressive increase of the inflammatory response and (2) decreased habituation to pain via progressive deterioration of the pain-inhibitory response.

This proposal will implement a research design consisting of 3 repetitions of a 4-day episode with 3 nights of experimentally-induced insomnia symptoms followed by 1 night of recovery sleep, thereby resembling frequently observed sleep patterns in individuals suffering from insomnia. I.e., after an interval of 1 to 3 nights of poor sleep, individuals experience a better night of sleep, likely resulting from a buildup of sleep pressure during the insomnia episode^{31,41}. The protocol will end with 4 nights of recovery sleep, in order to statistically model time to obtain full recovery of the inflammatory and pain-inhibitory system. The study will take place under controlled in-laboratory conditions in the Clinical Research Center, in order to ensure maintenance of sleep-wake schedules and minimize the influence of confounding variables such as food or fluid intake, light exposure, body posture and motor activity. Each protocol includes frequent blood draws, urine collections, and the administration of a complex pain testing battery on 8 out of the 18 in-hospital days.

Study Design.

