This study will employ an intra-individual balanced 2 x 18-day in-hospital protocol (experimental insomnia vs. control sleep condition, see **Figure 8**). The first 2 nights of each 18-day protocol will be adaptation nights, and the 3rd night will serve as the baseline night, with a sleep opportunity of 8 hours (23pm-7am) on all 3 nights. In the experimental insomnia study arm, insomnia symptoms will be induced during the next 3 nights, followed by 1 night of 8-hour recovery sleep (for more details, see model description under Procedures). During nights with insomnia symptom induction, sleep onset will be delayed by 1 hour (midnight 12am), the sleep period (12-6am) will be disrupted by hourly 20 min long awakenings, and sleep offset will be advanced by 1 hour (6am). This episode of 3 nights of experimental insomnia followed by 1 night of recovery sleep will be repeated three times. After the last experimental insomnia episode, participants will have 4 recovery nights. In the control arm of the study, participants will receive an 8-hour sleep opportunity for all 18 nights of the protocol. These 2 arms of the study will be separated by an interval of at least 1 month in order to allow recovery from blood sampling. Monthly separation was chosen to control for potential effects of menstrual phase in women. Depending on the bed occupancy space, participants will stay in a private room in the CRC. If a private room is not available, participants will stay in a double occupancy room with an individual of the same sex (assigned at birth)

Visit 1. Initial screening. All potential participants will have the study explained to them in detail by the PI or another senior member of the research team. If interested, potential participants will sign the informed consent and nursing staff in the Clinical Research Center (CRC) will take vital signs and collect a blood sample. A short battery of screening tests and questionnaires will also be collected in order to assess health status (see **Appendix 1** for blood tests and questionnaires). Potential participants will then be introduced to the web-based, secured diary recording system (REDCap²²) and given an actigraphy watch to take home to estimate sleep-wake habits, for 2 weeks (see **Appendix 1**). These data will be used to verify nightly sleep duration between 7 to 9 hours to be used for eligibility.

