Visit 2. Medical history, physical, and sleep screening. During this visit, the study physician will meet with the study participant for a physical exam and review of blood test results. Anemia and abnormal thyroid results are the most frequent exclusionary medical findings in our healthy volunteers. Participants who remain eligible following the medical screen will be instrumented for polysomnographic recording (PSG) for a sleep screening night in the CRC, in order to rule out any possible sleep disorders (see detailed exclusion criteria in Protection of Human Subjects).

Visit 3 and 4: Two 18-day in-hospital stays (experimental insomnia and sleep control condition). Throughout the 18-day **experimental insomnia condition** (see **Figure 8**), participants will start with 3 nights of adaptation/baseline nights, before undergoing 3 episodes of 3 nights of insomnia symptom induction followed by 1 night of 8 hours of sleep. Four recovery nights will follow the last experimental insomnia episode. During this 18-day period, participants will have 8 days of intensive recording (on the baseline night, every 2nd and 4th day of each episode, as well as the 3rd recovery night at the end of the protocol, see also **Figure 'Study Protocol'**). These intensive measurement periods will include PSG recordings, blood sampling, and urine collection during daytime (7am-11pm) and nighttime (11pm-7am) periods. Emotional and physical well-being will be assessed on computerized visual analog scales every 4 hours throughout waking periods (see **Appendix 2**) and a pain testing battery will be administered at 2pm (see **Appendix 3**). For the experimental insomnia nights, the sleep opportunity will be from 12am-6am (rather than 11pm-7am) with hourly 20min-awakenings. However, participants will remain in bed in a semi-supine position during the wakeful nighttime periods (11pm-12am, 20-min awakening bouts, 6am-7am), in order to maintain consistent postural and physical activity inputs across all study nights and conditions. Lights

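### The closing recovery nights are said to allow modelling of time to full recovery, but outcomes are recorded at only two points after the last insomnia night and no Aim 3 contrast compares the last point with baseline

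*Combined protocol and SAP*

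**What the plan says.** The Proposed Research Plan in B3.A gives the reason for the closing nights: "The protocol will end with 4 nights of recovery sleep, in order to statistically model time to obtain full recovery" of the two systems under study.

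Study Design sets out the stay. It opens with three nights: "The first 2 nights of each 18-day protocol will be adaptation nights, and the 3rd night will serve as the baseline night". The main block follows: "This episode of 3 nights of experimental insomnia followed by 1 night of recovery sleep will be repeated three times". Then: "After the last experimental insomnia episode, participants will have 4 recovery nights". The Visit 3 and 4 text repeats this: "Four recovery nights will follow the last experimental insomnia episode". In the control arm, "participants will receive an 8-hour sleep opportunity for all 18 nights of the protocol".

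Sleep recording, blood, urine and the pain battery are confined to eight intensive recording days. Visit 3 and 4 lists these as baseline, "every 2nd and 4th day of each episode, as well as the 3rd recovery night at the end of the protocol". The polysomnography paragraph and the Assessment of Aim 1 give the same set.

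The Assessment of Aim 3 compares days 3 and 7, 7 and 11, and 11 and 15. It then compares the average of days 7, 11 and 15 with day 17, and describes this last step as one recovery night against three.

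On what to expect, B2 reports that after a single episode of sleep restriction or total deprivation, IL-6 levels "do not normalize after one night or even two nights of recovery sleep".

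**The concern.** To estimate a time to full recovery, a trial needs a definition of full recovery, enough measurements on the way back to locate the return, and follow-up that lasts until the return has occurred. The plan defines neither full recovery nor a time-to-recovery endpoint, and it measures twice.

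Two things are at stake. First, a recovery time reported from these data would come mainly from the curve chosen to join the points, and from extrapolation if the outcome is still away from baseline at the last one. Second, the Aim 3 contrasts mostly compare recovery days with one another. The trial could show that three good nights do more than one and still not say whether the system is back where it started. B2 ties the practical message (prevent the changes, or treat them afterwards) to how reversible they are, so this answer is the one a reader will look for.

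**Working it through.** **Inputs.** Three adaptation and baseline nights, three episodes, four closing recovery nights and an 18-night stay (Study Design); eight recording days (Visit 3 and 4); days 3, 7, 11, 15 and 17 (Assessment of Aim 3).

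**The plan's own totals.** Take the recovery night after the third insomnia block as the first of the four closing nights:

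- nights 1–3: adaptation and baseline
- nights 4–6 insomnia, 7 recovery
- nights 8–10 insomnia, 11 recovery
- nights 12–14 insomnia
- nights 15–18 recovery

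The total is 3 + 4 + 4 + 3 + 4 = 18, as stated. The recorded nights are 3, 5, 7, 9, 11, 13, 15 and 17, which is 8, also as stated. Nights 15 and 17 match the Aim 3 day numbers and its one-versus-three-nights description.

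**What is recorded after the last insomnia night (14).** Nights 15 and 17 are recorded; nights 16 and 18 are not. Write k for the first recovery night on which the group is back at baseline, and assume that once back it stays back:

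| k | Recovered after 1 night? | Recovered after 3 nights? |
|---|---|---|
| 1 | yes | yes |
| 2 or 3 | no | yes |
| 4 or more | no | no |

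There are three distinguishable patterns. k = 2 cannot be told from k = 3, and nothing beyond 3 can be told apart. A straight line through two means has two parameters, so 2 − 2 = 0 degrees of freedom remain to check its shape.

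**Visit 5.** This is a blood draw and a review 7 to 14 days after both stays, with no pain battery described. In the insomnia-first sequence it follows the control stay, which starts at least a month after the insomnia stay. It does not extend the recovery curve.

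**What the Aim 3 contrasts test.** With m for the mean on a day, they are:

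- c1 = m7 − m3
- c2 = m11 − m7
- c3 = m15 − m11
- c4 = m17 − (m7 + m11 + m15)/3

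For IL-6, a negative c4 says that three nights leave a lower level than one. It is compatible both with full return and with a level still above baseline. The missing quantities are combinations of the listed ones:

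- m15 − m3 = c1 + c2 + c3
- m17 − m3 = c4 + [c1 + (c1 + c2) + (c1 + c2 + c3)]/3 = c4 + c1 + (2/3)c2 + (1/3)c3

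Both can therefore be estimated from the recorded days without new data, but neither is listed.

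**Why relative to control.** The Visit 3 and 4 text says that inflammatory markers have fallen during control sleep in the research unit in earlier studies. A return to the participant's own day 3 level could then partly reflect the stay itself. The Aim 1 analysis text allows either raw data or between-condition differences, and the Aim 3 text does not say which its contrasts use.

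**The case against.** The strongest reply is that the sentence in the Proposed Research Plan is a design rationale, not an aim or an endpoint. Aim 3 postulates progressively impaired return to baseline, and its listed contrasts are all supported by the recorded days. This stands: a reader might infer that Aim 3 as a whole cannot be delivered, and the documents do not support that. What remains is that the stated purpose is not met and that the last point is never compared with baseline.

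A second reply is that the main analysis is a mixed model over all eight recordings, with an optional one-knot piecewise fit for the prolonged recovery, so the final stretch does not rest on two points alone. This is partly right. The nearest earlier recording, however, is night 13, with one more insomnia night before recovery begins, and neither the model nor the knot adds an observation after night 17. Interpolation between nights 15 and 17 is possible under an assumed shape; any later time is extrapolation.

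A third reply is that the IL-6 statement in B2 concerns single episodes of a different exposure, and that a measurement after three nights goes beyond the two nights it mentions. That is fair. The statement makes incomplete recovery at the last point plausible; it does not predict it.

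A reader might also add 3 + 12 + 4 = 19 nights and see a contradiction with 18. The documents do not bear this out. The model description under Procedures uses the word episode for the three insomnia nights alone, and Aim 3's days 15 and 17 fit only the 18-night count. On the 19-night reading the third closing night would be night 18, and day 17 would not be recorded. The word is used in two senses, which is an ambiguity. It is not why the recovery time is out of reach: on either reading there are only two recorded points after the last insomnia night.

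**Conclusion.** The point holds in a limited form. Of the four closing recovery nights, two are recorded. The data can locate group-level recovery only as by the first night, during nights 2–3, or not by night 3, and cannot estimate a recovery time. None of the four listed Aim 3 contrasts compares day 17 with day 3, so full recovery is not tested as written. The listed contrasts stay valid for what they compare, and the point gives no reason to change the sample size.

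This rests on three assumptions: the 18-night schedule that the Aim 3 day numbers imply; recovery that does not reverse once reached; and measurements on days 15 and 17 that reflect one and three recovery nights, as the Aim 3 text says. The documents do not state whether a numbered day's testing comes before or after the night of the same number. If it came before, fewer recovery nights would lie behind each daytime value. The conclusion is about group means; the plan proposes no participant-level classification of recovery and gives no threshold for one.

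**What to change.** 1. In the Proposed Research Plan, replace the time-to-recovery purpose with: whether each outcome has returned to baseline, relative to control on the same day, after one and after three recovery nights.
2. In the Assessment of Aim 3, add two contrasts per outcome, day 15 minus day 3 and day 17 minus day 3, each as insomnia minus control and with a confidence interval. A non-significant difference should not by itself be read as recovery.
3. Report no estimated recovery time. Where it applies, state that the outcome was not shown to have recovered by the last recorded point.
4. As a minor clarification, say in Study Design and in Visit 3 and 4 whether the third episode's recovery night is the first of the four closing nights; the 18-night total and Aim 3's days 15 and 17 imply that it is. State also how day numbers relate to night numbers.

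No extra blood draws, visits or participants are needed. The cost is a narrower stated objective and two more contrasts per outcome to report.

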In case of last-minute cancellations of the 18-day in-hospital stays, we will attempt to fill the open slots with new participants. We will use adaptation day 1 of the study for screening purposes (i.e., initial and medical/overnight screening), and if fulfilling screening criteria, the participant will continue the following day with adaptation day 2 of the study.

Visit 5: Follow-up. Seven to 14 days following their final discharge from the CRC (after completing both study protocols), participants will return to the CRC to have a final blood draw to ensure that any potential activation of the blood markers have returned to baseline and to review their study experience.

Participants.

We anticipate screening 612 subjects in order to have 34 participants with an attrition rate of 32% complete both 18-day in-hospital study protocols. We typically screen 18 potential participants for every one that enters the in-hospital part of the study. In our experience with 2 25-day in-hospital stays separated by a monthly interval, we have an attrition rate of 32%. As such, 34 participants will need to enter the hospital phase to have 26 participants complete 2 18-day in-hospital protocols.

Procedures.

Model of repeated exposure to experimentally-induced insomnia symptoms. The hypothesis will be tested within an experimental insomnia model characterized by (1) induction of insomnia symptoms for 3-day long episodes, and (2) the repeated nature of such insomnia episodes, i.e. after a night of good sleep, the next episode will start. Participants will undergo 3 of those 3-day episodes of insomnia symptom induction, each followed by 1 night of 8 hours of sleep. Such patterns are

commonly experienced in individuals suffering from insomnia, where intervals of 1 to 3 nights of poor sleep are followed by a night of good sleep, likely due to the buildup of sleep pressure during the interval of poor sleep^{31;41}. The advantage of this approach is that it mimics sleep-wake patterns frequently found in the general population for a number of reasons, and in chronic pain populations in particular^{28;39}. In contrast to previous studies, mostly using single episodes of sleep restriction or deprivation, this approach will facilitate the translation of findings directly into clinical applications.

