The Cold Pressor Test (CPT): This test requires the insertion of the hand into an ice-cold water bath (Techne® water baths, Bibby Scientific US, Burlington, NJ) held at a temperature of 3°C. Participants are instructed to leave their hand in the water bath for at least 1 minute and are told that they may remove their hand earlier if the pain gets unbearable. Maximum immersion time will be 3 minutes. Pain intensity and unpleasantness will be rated every 10 sec during the hand immersion, as well as every 10 sec for 2 minutes and 30 seconds post-testing to capture recovery slopes.

Statistical Considerations

Sample size: 34 subjects (including a 32% discontinuation rate) will run in balanced order through the two protocols, each consisting of a 18-day in-hospital stay (separated by an interval of 1 month or more) in order to complete the study with 26 subjects. **Power calculations** for the inflammatory response (aim 1) were estimated using findings coming from sleep restriction models on IL-6 (plasma levels and expression by monocytes). For the pain-inhibitory response (aim 2), we estimated power using the effects of a single episode of sleep disruption on the pain-inhibitory capacity³⁷. For the recovery response (aim 3), we used data from the effects of recovery sleep on IL-6 positive monocytes, as well as on the habituation to pain in the cold pressor test paradigm (data obtained in currently ongoing protocol). For all 3 aims, optimal power will be reached with a sample size of N=26 (see **Table 1**).

Randomization: Block randomization will be used with block sizes of 10, 8, 8, and 8. Each block will have equal numbers of females and males and equal numbers of sequences (1. insomnia induction – control sleep, 2. control sleep – insomnia induction). Randomization will be prepared by the study statistician and the participant will be informed of the sequence on study day 1.

Statistical Analysis:

Table 2 shows the primary outcome variables for aim 1-3, as well as secondary outcome variables used for explorative analysis (not part of aims).

Some of the variables will be measured at different time scales and reduced to the following summary variables: Subjective estimations of emotional and physical well-being assessed every 4 hours during the waking periods (and after each nighttime awakening during insomnia induction nights) of the protocol will be averaged to nighttime and daytime frequency and intensity measures.

Table 2: Outcome variables			

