Primary outcomes			Secondary outcomes
Aim 1	Aim 2	Aim 3	Explorative
Inflammatory: IL-6, PGE2, resolvins	Pain-inhibitory: CPM	IL-6, PGE2, resolvins, CPM	COX-2, cortisol
Sensitization: HPT, PPT, TS	Habituation: Intensity ratings of HPST	HPT, PPT, TS, HPTS	Emotional/physical well-being
HPT= heat pain threshold; PPT=pressure pain threshold, TS=temporal summation; HPST=heat pain supra- threshold, CPM=conditioned pain modulation, COX=cyclooxygenase			

Table 1: Power calculations.

Variable	Δ Response	Power based on paired Student t-test (α=0.05) – N=26
IL-6 (pg/mL). Response to 10 days of restricted sleep to 4h/night compared to 8h control sleep.	1.95±1.59 pg/ml	>0.80
IL-6 positive monocytes (%). Response to three cycles of sleep restriction (3 x 5 nights of 4 hours of sleep/night), compared to 8h control sleep (ongoing protocol R01 HL 105544, see also Figure 3).	38±66 %	>0.80
Pain inhibition impairment (CPM test, %). Response to 3 days of experimental sleep disruption, compared to control sleep (estimation from graph) ³⁷ .	47±54 %	>0.80

Habituation to pain (CPT test, sec). Response to 3 cycles of sleep restriction (3 x 5 nights of 4 hours of sleep/night), on the ability to habituate to cold pain, compared to 8h control sleep (ongoing protocol R01 HL 105544, see also Figure 7).	-15±25 sec	>0.80
Habituation to pain after recovery sleep (CPT test, sec). Response to 2 recovery nights following 3 cycles of sleep restriction on the ability to habituate to cold pain, compared to 8h control sleep (ongoing protocol R01 HL 105544, see also Figure 7).	-24±28 sec	>0.80

Assessment of Aim 1: Inflammatory response and its relation to indicators of sensitization of the nociceptive system upon repeated episodes of experimentally-induced insomnia symptoms:

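### At the stated 32% attrition, 34 entrants give about 23 expected completers, not the 26 on which the Table 1 power rests

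*Combined protocol and SAP*

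**What the plan says.** Three sections pair 34 participants with a 32% loss.

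- **B3.A, Participants.** The rate comes from an earlier protocol with two 25-day stays a month apart. From it the section concludes: "As such, 34 participants will need to enter the hospital phase to have 26 participants complete 2 18-day in-hospital protocols". The opening sentence of the same section reads differently, as if all 34 finish: "We anticipate screening 612 subjects in order to have 34 participants with an attrition rate of 32% complete both 18-day in-hospital study protocols".
- **Statistical Considerations, Sample size.** "34 subjects (including a 32% discontinuation rate) will run in balanced order through the two protocols", with 26 subjects completing. Power then rests on the completers: "For all 3 aims, optimal power will be reached with a sample size of N=26".
- **C. Subject Selection.** Total enrolment is 34, 17 of them women, again described as including 32% discontinuation.

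Two other design figures depend on 34. The randomisation blocks of 10, 8, 8 and 8 sum to 34, and the screening target is 18 per entrant (34 × 18 = 612).

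Table 1 gives power above 0.80 in all five rows at N=26 and α=0.05, under the column heading "Power based on paired Student t-test". It does not say whether the test is one- or two-sided.

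On replacement, the Study Design section says of last-minute cancellations that "we will attempt to fill the open slots with new participants".

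**The concern.** An attrition rate is a fraction of those who enter, so the number of entrants is the number of completers divided by one minus the rate. The plan's 34, 26 and 32% do not satisfy that relation. No calculation is shown. The figure 34 is what results from multiplying 26 by 1.32, which applies the rate to completers instead of entrants.

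The Table 1 calculation needs both stays from each participant, so it depends on completers. If the protocol's own rate holds, the trial should expect about three fewer than the number that supports every power statement. The question is whether the entries above 0.80 survive that.

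**Working it through.** **Inputs.** Attrition 32%, 34 entrants and 26 completers (B3.A Participants; Sample size; C. Subject Selection). Effects and SDs, α=0.05 and the paired t-test from Table 1. Sidedness is not given, so both readings are shown.

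**The plan's own figure**

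- Entrants needed for 26 completers at 32% loss: 26/(1 − 0.32) = 38.2, so 39. The stated 34 is not reproduced.
- Multiplying instead: 26 × 1.32 = 34.3. This matches 34, but that origin is an inference.

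**Forward check**

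- Expected completers from 34: 34 × 0.68 = 23.1.
- Attrition implied by 34 and 26: 1 − 26/34 = 8/34 = 23.5%.
- Chance of 26 or more completers, taking losses as independent: P(Bin(34, 0.68) ≥ 26) = 0.19.

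**Power.** Paired t-test with the noncentral t distribution: standardised effect d = |Δ|/SD, noncentrality d√N, N − 1 degrees of freedom.

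| Table 1 row | d | Two-sided, N=26 | Two-sided, N=23 | One-sided, N=23 |
|---|---|---|---|---|
| Plasma IL-6 | 1.95/1.59 = 1.226 | >0.99 | >0.99 | >0.99 |
| IL-6 positive monocytes | 38/66 = 0.576 | 0.806 | 0.751 | 0.848 |
| CPM impairment | 47/54 = 0.870 | 0.989 | 0.979 | 0.992 |
| Cold pressor habituation | 15/25 = 0.600 | 0.836 | 0.785 | 0.873 |
| Cold pressor after recovery | 24/28 = 0.857 | 0.987 | 0.975 | 0.990 |

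The N=26 column reproduces every Table 1 entry on a two-sided reading.

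The smallest N reaching 0.80 is 26 two-sided (21 one-sided) for monocytes, and 24 two-sided (19 one-sided) for cold pressor habituation. The monocyte row therefore has no slack two-sided: at N=25 its power is 0.789.

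Averaging power over the binomial number of completers from 34, instead of fixing N at 23, changes little. Monocytes give 0.749 two-sided and 0.845 one-sided; cold pressor habituation gives 0.782 and 0.870.

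**The case against.** The arithmetic mismatch is hard to dispute. The case on the other side concerns how much it matters.

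- **Sidedness.** Table 1 does not state it, and the hypotheses are directional. One-sided, every row stays at or above 0.848 at N=23 and no Table 1 entry becomes false. This stands as a limit. Two-sided is the usual convention, and 26 is exactly the two-sided minimum for the monocyte row. The plan does not say which row set N, however, so that match is suggestive only.
- **Size.** Two-sided, the affected rows lose about 0.05, and all the effects are borrowed from other protocols. One affected row, cold pressor habituation, is a planning proxy absent from Table 2. This stands. The monocyte row is less easily set aside: Table 2 lists IL-6 without restricting it to plasma, and the Sample size section names the monocyte measure as a power basis for Aims 1 and 3.
- **Shorter stays and refilled slots.** The 32% comes from 25-day stays, so loss over 18 days may be lower, and cancelled slots may be refilled. Both could raise the number of completers. Neither is quantified or used to justify 34. Refilling is only an attempt and covers only last-minute cancellations, while the Sample size and Subject Selection sections adopt 32% for this trial.
- **Mixed model.** The main analysis can use participants with one stay, and several contrasts named for Aims 1 and 3 lie within a stay. That softens the loss for those contrasts. It does not restore the paired comparison between conditions on which Table 1 rests, nor the stated 26.

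**Conclusion.** The concern holds. As written, 34 entrants, 26 completers and 32% attrition are incompatible: the plan's own rate gives about 23 completers, and 26 would be reached with probability 0.19 if losses are independent.

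The effect on power is modest and conditional. Assuming a two-sided test and Table 1's effect sizes, two of the five rows fall below the claimed 0.80, to about 0.75 (monocytes) and 0.785 (cold pressor habituation). The plasma IL-6 and CPM rows are essentially unaffected. Under a one-sided test no row falls below 0.80. This does not show that the trial is unable to meet its aims. The sample size justification should be corrected because a stated planning number does not follow from its inputs.

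**What to change.** Choose one of two corrections.

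1. Keep 34 entrants and 32%, state about 23 expected completers, give the sidedness of the test and recompute Table 1. Two-sided, the figures that change materially are about 0.75 for monocytes and 0.785 for cold pressor habituation.
2. Keep 34 and 26, and state and justify a planning attrition of about 23.5% for the 18-day stays, explaining why it is lower than in the 25-day stays. Give the sidedness here too.

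Use the same figures in B3.A Participants, the Sample size paragraph and C. Subject Selection. Under the first option, also revise the count of twenty-six participants in B1, the statement that power is reached at N=26, and the N=26 in the Table 1 heading. Under either option, reword the opening Participants sentence, which reads as if 34 complete. It would also help to say whether IL-6 in Table 2 includes the monocyte measure.

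The cost is wording, one statement of sidedness and, under the first option, two lower power figures. Procedures and recruitment do not change.

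For reference only: 26 expected completers at 32% needs at least 39 entrants (39 × 0.68 = 26.5). Keeping sexes and sequences equal takes 40, which means 40 × 18 = 720 screened and 40 × 0.68 = 27.2 expected completers.
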